Multicenter open post-registration study of the safety and effectiveness of the medical device HBIS endoprosthesis of synovial fluid NOLTREX[™] for intraarticular administration in the treatment of gonarthrosis.

Protocol number

IA/PAAG-SI/OA/2020

Studied MD

HBIS endoprosthesis of synovial fluid NOLTREXTM according to TU 9398-00152820385-2015 (hereinafter referred to as NOLTREXTM)

Comparison MD

Not applicable

The duration of the study, the number of research centers and patients

From 29.05.2020 to 31.05.2021, the number of research centers is 4.

Number of patients: a maximum of 72

Purpose of research

Evaluation of the safety and effectiveness of the medical device (MD) NOLTREX[™] for intraarticular administration in the treatment of gonarthrosis of the II–III x–ray stage according to Kellgren-Lawrence.

Tasks of research

1. Evaluation of the safety of MD NOLTREXTM at intraarticular administration in the treatment of gonarthrosis of the II-III radiological stage by Kellgren-Lawrence;

2. Evaluation of the effect of MD NOLTREXTM at intraarticular administration in the treatment of Kellgren-Lawrence stage II–III gonarthrosis on knee function and the need for paracetamol and non-steroidal anti-inflammatory drugs (NSAIDs).

Research method

Study design:

Open-label interventional study in one group with gonarthrosis patients who received a single or double course of injections of MD NOLTREXTM as part of the IA/PAAG-SI/OA/2019 study.

MD NOLTREXTM (synovial fluid endoprosthesis) has been registered for the treatment of osteoarthritis since 2003, and according to annual post-marketing observations it is an effective and safe medical device. A multicenter, double-blind, randomized, comparative, placebo-controlled study of the efficacy and safety of NOLTREXTM for intraarticular administration in the treatment of

gonarthrosis (IA/PAAG-SI/OA/2019) was conducted, in which 72 patients aged over 50 years with a verified diagnosis of gonarthrosis in accordance with the criteria of the American College of Rheumatology (ACR) II-III radiological stage classification Kellgren-Lawrence received 1 to 2 injections (at 1-week intervals) of 4 mL of MD NOLTREXTM into the most affected (target) knee joint. The second injection was not performed if the severity of pain in the target knee joint decreased by 40— or more a week after the first injection. The study was performed to evaluate the effectiveness and safety of MD NOLTREXTM with this method of use in comparison with placebo.

The current study is planned to include patients who received at least one intra-articular injection of MY NOLTREX[™] in IA/PAAG-SI/OA/2019 study and underwent procedures during the 5-week Visit (25 weeks – 6 months after the injection). After completing all the procedures of Visit 5 and completing the corresponding electronic individual registration card (eCRF) forms in the IA/PAAG-SI/OA/2019 study, the investigator receives information about which group in the IA/PAAG-SI/OA/2019 study the patient was assigned to, i.e. whether he received injections of the study MD or placebo. After that, patients who received the studied MD will be asked to sign an informed consent form to participate in the open clinical trial IA/PAAG-SI/OA/2020.

Procedures of Visit 5 (25 weeks - 6 months after injection) of the placebo-controlled trial IA/PAAG-SI/OA/2019, if they coincide with the screening procedures of Visit 0 of the open trial IA/PAAG-SI/OA/2020 for patients who have agreed to participate in this study and are eligible to participate, will be considered as procedures Visit 0 of the open trial IA/PAAG-SI/OA/2020. Thus, Visit 5 of the IA/PAAG-SI/OA/2019 study coincides with the screening Visit (Visit 0) of the IA/PAAG-SI/OA/2020 study.

Patients who signed the informed consent form to participate in an open study IA/PAAG-SI/OA/2020 to evaluate the safety and effectiveness of MD NOLTREXTM, in the case when pain in the target knee joint in the study IA/PAAG-SI/OA/2019 remained the same or increased (on a 100-mm visual analogue scale [VAS]) compared to the rating at Visit 1 of the study IA/PAAG-SI/OA/2019 (or if a decrease in pain severity is less than 40— compared to the rating at Visit 1 of the study IA/PAAG-SI/OA/2019), will receive the injection of MD NOLTREXTM in the target knee (Group A). MD will be administered in accordance with the instructions for use of MD NOLTREXTM: 4.0 ml per injection (2.5 + 1.5 ml, or 2.0 + 2.0 ml from two syringes through one needle [one puncture]) at intervals of one week. The course in an open study is a maximum of 2 injections (the first - at Visit 1, the second - at Visit 2). The number of injections is determined by the doctor depending on the stage of gonarthrosis and the clinical response. In order to avoid overfilling the joint with dense slowly resorbable material, at the good clinical result (reducing the pain severity on a 100 mm VAS by Visit

2 by more than 40— compared to the basal level in the open study[1]), the course of injections will be discontinued.

Patients included in the open part of the study, who have the severity of pain in the target knee joint at the time of inclusion in the open part of the study decreased by 40— or more compared to the assessment on Visit 1 of the IA/PAAG-SI/OA/2019 study, or those who cannot be re-injected with MD NOLTREXTM, a re-injection of MD NOLTREXTM will not be performed on Visits 1 and 2 of the open study (Group B).

A repeated course of MD NOLTREXTM injections in an open study is not possible if any of the following criteria are met:

- 1. Documented intolerance of the studied MD NOLTREXTM;
- 2. Active inflammation in the target knee joint (edema, hyperemia, effusion) at the time of inclusion in the study;
- 3. Inflammatory diseases of the skin and soft tissues in the area of the intended introduction of the studied MD into the target joint;
- 4. History of venous thrombosis and thromboembolism;
- 5. Deviations from the norm in the coagulogram (activated partial thromboplastin time [APTT], prothrombin time [PT], prothrombin index, fibrinogen);
- 6. Hemophilia and other hemorrhagic diatheses, as well as taking anticoagulants and disaggregants;
- Inflammatory changes in clinical blood analysis (leukocytosis, increased erythrocyte sedimentation rate [ESR]);
- 8. Deviation from the norm (in accordance with the standards of the local laboratory) of the number of platelets;
- 9. Type 1 or type 2 diabetes;
- 10. Acute infectious diseases or infectious exacerbations of chronic diseases (including respiratory tract infections) during the month prior to inclusion in the study.

At Visit 3 additional evaluation will be conducted to assess the feasibility and possibility of reinjections with MD NOLTREXTM among patients of group B. If at Visit 3 of the open study pain remains the same in the target joint of the study IA/PAAG-SI/OA/2019 or increases in intensity (as per 100-mm VAS) in comparison with the assessment at Visit 1 of the study IA/PAAG-SI/OA/2019 (or if a decrease in pain severity is less than 40% when compared to the rating at Visit 1 of the study IA/PAAG-SI/OA/2019), in the absence of the above criteria for non-treatment with the studied MD, at Visit 3 of open study the injection of MD NOLTREXTM into the target knee joint will be performed. MD will be administered in accordance with the instructions for medical use of MD NOLTREXTM: 4.0 ml per injection (2.5 + 1.5 ml, or 2.0 + 2.0 ml from two syringes through one needle [one puncture]) once or twice at intervals of one week. The treatment course in the framework of an open study among patients of Group B is a maximum of 2 injections (the first - at Visit 3, the second - at Visit 4). The number of injections is determined by the doctor depending on the stage of gonarthrosis and the clinical response. In order to avoid overfilling the joint with dense slowly resorbable material, at the good clinical result (reducing the pain severity on a 100 mm VAS by Visit 2 by more than 40— compared to the basal level in the open study[1]), the course of injections will be discontinued. The open nature of the study in one group is determined by the main purpose of the study - to assess the safety of MD NOLTREX[™] with a single or repeated course of use. Placebo safety data at the 6-month point (visit 5) in the IA/PAAG-SI/OA/2019 study will be used as a control. It is assumed that continued monitoring of patients in the placebo group will not lead to the detection of new adverse events (AE), the frequency of which should be compared with the frequency in the active therapy group, and is connected to unethical restriction of patients in the placebo group in the possibility of using potentially effective synovial fluid endoprostheses.

The open study provides follow-up of patients for 6 months (up to 25 weeks from Visit 1).

Thus, the maximum duration of participation in the study for one patient will be a maximum of 172 days.

Patient visits

Visit 0 (Day 0, -24 h -0 h, screening)

Procedures at Visit 5 of study IA/PAAG-SI/OA/2019 (hereinafter referred to in the Protocol as Clinical study 1 - CS1) that coincide with the screening Visit procedures (Visit 0) in study IA/PAAG-SI/OA/2020 will be counted as the procedures of Visit 0 of study IA/PAAG-SI/OA/2020, there is no need to repeat the identical procedures of these visits.

- The signing of the informed consent;
- The collection of demographic data;
- Measurement of the body weight;
- Collection of complaints and anamnesis;
- Registration of concomitant therapy;
- Assessment of the main vital signs (blood pressure [BP], heart rate [HR], number of respiratory movements [RR], body temperature);
- Physical examination of joints;

- Completing an algofunctional questionnaire for evaluating the osteoarthritis index developed by researchers at the Western Ontario and McMaster Universities Osteoarthritis, WOMAC with an assessment of subscale pain (WOMAC-A), stiffness (WOMAC-B), and functional performance (WOMAC-C) (from *Visit 5 of CS1*);
- Assessment of the severity of pain in the target knee joint by 100-mm VAS (from *Visit 5 of CS1*);
- Evaluation of the effectiveness of treatment by the patient, parameter OEP (from *Visit 5 of CS1*);
- Evaluation of the effectiveness of treatment by the investigator, parameter OEI (from *Visit* 5 of CS1);
- Documenting the target knee joint (the same joint that was identified as the target in the IA/PAAG-SI/OA/2019 study);
- Clinical blood test (hemoglobin level, hematocrit, red blood cell count, white blood cell count, white blood cell formula, platelet count, ESR) (from *Visit 5 of CS1*);
- Biochemical analysis of blood (glucose, alanine aminotransferase [SPGT], aspartate aminotransferase [AST], alkaline phosphatase [ALP], gamma-glutamyltranspeptidase [GGTP], total bilirubin, creatinine, uric acid, rheumatoid factor) (from *Visit 5 of CS1*);
- Coagulogram (APTT, PT, prothrombin index, fibrinogen) (from *Visit 5 of CS1*);
- Blood tests for antibodies to human immunodeficiency virus (HIV), hepatitis b surface antigen (HBsAg) and antibodies to Hepatitis C Virus (anti-HCV]), syphilis (RW);
- General urinalysis (color, transparency, relative density, pH, glucose, protein, ketone bodies, urobilinogen) (from *Visit 5 of CS1*);
- Rapid urine test for pregnancy in women with preserved reproductive potential (from *Visit* 5 of CS1);
- Evaluation of inclusion/non-inclusion criteria;
- Issuing a patient's diary;
- Check AE and serious AE (SAE).

Visit 1 (Week 0, Day 1, start of treatment)

- Measurement of the body weight;
- Collection of complaints and anamnesis;
- Registration of concomitant therapy;

- Assessment of the main vital signs (BP, HR, RR, body temperature);
- Physical examination of joints;
- Evaluation of inclusion/non-inclusion criteria;
- Injection of the studies MD into the cavity of the target joint (only for group A patients who are shown to receive the injection in accordance with the criteria specified in the Protocol);
- Registration of AE and SAE;
- Evaluation of exclusion criteria.

Every 2 weeks between Visit 1 and Visit 3 (weeks 3, 5, 7, 9 and 11), telephone contacts are made with the patient to clarify complaints, AE and the need for taking paracetamol or NSAIDs for the past 2 weeks. If AE is detected, or the need to take paracetamol or NSAIDs more than 4 days a week in each of the consecutive 2 weeks, the patient is invited to the clinic for an unscheduled Visit or a Visit to prematurely complete participation in the study (depending on the reason for the visit).

Visit 2 (Week 1, Day 8, treatment and follow-up) - as indicated

Only patients who received an injection of MD NOLTREXTM into the target knee joint on Visit 1 are eligible for Visit 2.

The following procedures must be performed during the visit:

- Measurement of the body weight;
- Collection of complaints and anamnesis;
- Registration of concomitant therapy;
- Assessment of the main vital signs (BP, HR, RR, body temperature);
- Physical examination of joints;
- Assessment of the severity of pain in the target knee joint using 100-mm VAS;
- Injection of the studied MD into the target joint cavity (only for patients of group A, in which the severity of pain in the target knee joint using 100 mm VAS did not decrease by 40% or more compared to the assessment on the Visit 0);
- Evaluation of the patient's diary;
- Return of the diary to the patient;
- Registration of AE and SAE;
- Evaluation of exclusion criteria.

Visit 3 (Week 13, Day 84 ± 2, treatment and follow-up)

- Measurement of the body weight;
- Collection of complaints and anamnesis;
- Registration of concomitant therapy;
- Assessment of the main vital signs (BP, HR, RR, body temperature);
- Physical examination of joints;
- Filling out algofunctional questionnaire WOMAC with an assessment of the subscales of pain (WOMAC-A), stiffness (WOMAC-B) and functional performance (WOMAC-C);
- Assessment of the severity of pain in the target knee joint using 100-mm VAS;
- Evaluation of the effectiveness of treatment by the patient, OEP parameter;
- Evaluation of the effectiveness of treatment by the investigator, OEI parameter;
- Clinical blood test (hemoglobin level, hematocrit, red blood cell count, white blood cell formula, platelet count, ESR);
- Biochemical blood test (glucose, ALT, AST, ALP, GGTP, total bilirubin, creatinine, uric acid, rheumatoid factor);
- Coagulogram (APTT, PT, prothrombin index, fibrinogen)
- General urinalysis (color, transparency, relative density, pH, glucose, protein, ketone bodies, urobilinogen);
- Injection of the studied MD into the cavity of the target joint (only for patients of Group B who are shown to receive the injection according to the criteria specified in the Protocol, and didn't receive the injection at Visit 1);
- Evaluation of the patient's diary;
- Evaluation of the total number of paracetamol tablets taken (one tablet = 500 mg) using patient's diary, PARACETAMOL parameter;
- Evaluation of the patient's diary of the total number of NSAIDs allowed by the Protocol in case of paracetamol inefficiency (NSAIDs allowed by the Protocol in case of paracetamol inefficiency: diclofenac potassium tablets 50 mg, diclofenac sodium tablets 75 mg, naproxen tablets 500 mg, naproxen sodium tablets 550 mg, meloxicam tablets 7.5 mg, celecoxib tablets 200 mg), NSAID parameter;
- Issuing a new patient diary to the patient;
- Registration of AE and SAE;
- Evaluation of exclusion criteria.

Every 2 weeks, between Visit 3 and Visit 4 (weeks 15, 17, 19, 21 and 23), telephone contacts are made with the patient to clarify complaints, AE and the need for taking paracetamol or NSAIDs for the past 2 weeks. If AE is detected, or the need to take paracetamol or NSAIDs more than 4 days a

week in each of the consecutive 2 weeks, the patient is invited to the clinic for an unscheduled Visit or a Visit to prematurely complete participation in the study (depending on the reason for the visit).

Visit 4 (Week 14, Day 91 ± 2, treatment and follow-up) - as indicated

Only patients who received an injection of MD NOLTREXTM into the target knee joint on Visit 3 are eligible for Visit 4.

The following procedures must be performed during the visit:

- Measurement of the body weight;
- Collection of complaints and anamnesis;
- Registration of concomitant therapy;
- Assessment of the main vital signs (BP, HR, RR, body temperature);
- Physical examination of joints;
- Assessment of the severity of pain in the target knee joint using 100-mm VAS;
- Injection of the studied MD into the target joint cavity (only for patients of Group B, in which the severity of pain in the target knee joint using 100 mm VAS did not decrease by 40% or more compared to the assessment at Visit 3)
- Evaluation of the patient's diary;
- Return of the diary to the patient;
- Registration of AE and SAE;
- Evaluation of exclusion criteria.

Visit 5 (Week 25, Day 169 ± 2 , follow-up)

- Measurement of the body weight;
- Collection of complaints and anamnesis;
- Registration of concomitant therapy;
- Assessment of the main vital signs (BP, HR, RR, body temperature);
- Physical examination of joints;
- Radiography of the knee joints and documentation of parameters of joint space width (JSW) and joint space narrowing (JSN);
- Filling out algofunctional questionnaire WOMAC with an assessment of the subscales of pain (WOMAC-A), stiffness (WOMAC-B) and functional performance (WOMAC-C);

- Assessment of the severity of pain in the target knee joint using 100-mm VAS;
- Evaluation of the effectiveness of treatment by the patient, OEP parameter;
- Evaluation of the effectiveness of treatment by the investigator, OEI parameter;
- Clinical blood test (hemoglobin level, hematocrit, red blood cell count, white blood cell formula, platelet count, ESR);
- Biochemical blood test (glucose, ALT, AST, ALP, GGTP, total bilirubin, creatinine, uric acid, rheumatoid factor);
- Coagulogram (APTT, PT, prothrombin index, fibrinogen);
- General urinalysis (color, transparency, relative density, pH, glucose, protein, ketone bodies, urobilinogen);
- Evaluation of the patient's diary;
- Evaluation of the total number of paracetamol tablets taken (one tablet = 500 mg) using patient's diary, PARACETAMOL parameter;
- As per patient's diary, evaluation of the total number of NSAIDs allowed by the Protocol in case of paracetamol inefficiency (NSAIDs allowed by the Protocol in case of paracetamol inefficiency: diclofenac potassium tablets 50 mg, diclofenac sodium tablets 75 mg, naproxen tablets 500 mg, naproxen sodium tablets 550 mg, meloxicam tablets 7.5 mg, celecoxib tablets 200 mg), NSAID parameter;
- Registration of AE and SAE;
- Evaluation of exclusion criteria.

An unscheduled visit

The following procedures must be performed during the visit:

- Measurement of the body weight
- Collection of complaints and anamnesis;
- Registration of concomitant therapy;
- Assessment of the main vital signs (BP, HR, RR, body temperature);
- Physical examination of joints;
- Evaluation of the patient's diary;
- Registration of AE and SAE;
- Evaluation of exclusion criteria.

At the time of unscheduled Visit, any of the research procedures can be additionally performed by the decision of the Chief investigator.

Visit to the prematurely end the participation in the study

The following procedures must be performed during the visit:

- Measurement of the body weight
- Collection of complaints and anamnesis;
- Registration of concomitant therapy;
- Assessment of the main vital signs (BP, HR, RR, body temperature);
- Physical examination of joints;
- Filling out algofunctional questionnaire WOMAC with an assessment of the subscales of pain (WOMAC-A), stiffness (WOMAC-B) and functional performance (WOMAC-C);
- Assessment of the severity of pain in the target knee joint on a 100-mm visual-analog scale (100-mm VAS);
- Evaluation of the effectiveness of treatment by the patient, OEP parameter;
- Evaluation of the effectiveness of treatment by the investigator, OEI parameter;
- Clinical blood test (hemoglobin level, hematocrit, red blood cell count, white blood cell formula, platelet count, ESR);
- Biochemical blood test (glucose, ALT, AST, ALP, GGTP, total bilirubin, creatinine, uric acid, rheumatoid factor);
- Coagulogram (APTT, PT, prothrombin index, fibrinogen);
- General urinalysis (color, transparency, relative density, pH, glucose, protein, ketone bodies, urobilinogen);
- Rapid urine test for pregnancy in women with preserved reproductive potential;
- Evaluation of the patient's diary;
- Evaluation of the total number of paracetamol tablets taken (one tablet = 500 mg) using patient's diary, PARACETAMOL parameter;
- As per patient's diary, evaluation of the total number of NSAIDs allowed by the Protocol in case of paracetamol inefficiency (NSAIDs allowed by the Protocol in case of paracetamol inefficiency: diclofenac potassium tablets 50 mg, diclofenac sodium tablets 75 mg, naproxen tablets 500 mg, naproxen sodium tablets 550 mg, meloxicam tablets 7.5 mg, celecoxib tablets 200 mg), NSAID parameter;
- Registration of AE and SAE;
- Evaluation of exclusion criteria.

The main parameters of evaluation of efficacy and safety

Basic safety parameters:

- 1. The frequency of AE and/or SAE;
- 2. Overall assessment of the tolerability of therapy by the investigator and the patient;
- 3. The main parameters of vital signs (HR, BP, RR, body temperature)
- 4. Results of physical examination;
- 5. Results of laboratory and instrumental examination.

Separately, it is planned to evaluate the cumulative (in the framework of a double-blind and open study) frequency of the most likely complications associated with periprocedural or temporary postprocedural (no more than 72 hours) pain or burning. These AE can be stopped with paracetamol or non-steroidal anti-inflammatory drugs.

Other possible side effects and complications of special interest related to the method of administration by intra-articular injection:

- pain or swelling at the injection site, feeling of bursting, burning, arthralgia, effusion in the joint, synovitis, aseptic acute arthritis;
- infections (pyogenic arthritis, direct infection of the joint at infectious diseases, osteomyelitis, sepsis, etc.);
- subcutaneous neuropathies, drug-induced vascular embolism.

It is assumed that the AEs are divided into groups: somatic AEs and AEs associated with the pathology of the target joint, as well as the frequency of both these groups and each AE, according to the following classification:

- Very common $\geq 10\%$;
- Common (frequent) < 10%, but $\ge 1\%$;
- Uncommon < 1%, but \geq 0.1%;
- Rare < 0.1%, but \ge 0.01%;
- Very rare < 0.01%.

The main parameters of the effectiveness of the studied MD:

- Change in the overall score on the WOMAC scale (WOMAC-T) at Visit 3 (week 13), Visit 5 (week 25) compared to the basal value at Visit 0 (screening) of the open study and compared to the basal value at Visit 1 (week 1) of the IA/PAAG-SI/OA/2019 study;
- Change in the pain subscale score (WOMAC-A) at Visit 3 (week 13), at Visit 5 (week 25) compared to the basal value at Visit 0 (screening) of the open study and compared to the basal value at Visit 1 (week 1) of the IA/PAAG-SI/OA/2019 study;

- Change in the score for stiffness subscale (WOMAC-B) and functional performance (WOMAC-C) at Visit 3 (week 13), Visit 5 (week 25) compared to the basal value at Visit 0 (screening) of open study and compared to the basal value at Visit 1 (week 1) of the study IA/PAAG-SI/OA/2019;
- 4. The change in the severity of pain in the target knee on a 100-mm visual analogue scale (100 mm VAS) at Visit 2 (week 1), Visit 3 (week 13), Visit 5 (week 25) compared to the basal value at Visit 0 (screening) open security research and compared to the basal value at Visit 1 (week 1) study IA/PAAG-SI/OA/2019;
- Evaluation of the effectiveness of treatment by the patient, parameter (on a scale from 1-clear deterioration to 6-significant improvement) on Visits 3 and 5 (parameters OEP-w₁₃ and OEPw₂₅, respectively);
- Evaluation of the effectiveness of treatment by the investigator, parameter (on a scale from 1clear deterioration to 6-significant improvement) on Visits 3 and 5 (parameters OEI-w₁₃, OEIw₂₅, respectively);
- Assessment of the total number of paracetamol tablets taken (one tablet = 500 mg) starting from day 1 at Visit 3 and 5 (parameters PARACETAMOL-w₁₃ and PARACETAMOL-w₂₅, respectively);
- Assessment of the total number of NSAID tablets taken starting from day 1 at Visits 3 and 5 (parameters NSAID-w₁₃ and NSAID-w₂₅, respectively);
- 9. The parameter JSN of the target knee joint at Visit 5 of the open study compared to the basal value on Visit 0 of the IA/PAAG-SI/OA/2019 study retrospectively.

All performance parameters will be analyzed among all patients included in open study no. IA/PAAG-SI/OA/2020, as well as in subgroups of patients:

- who received only one course of injections in the placebo-controlled study IA/PAAG-SI/OA/2019;
- those who received two courses of therapy both in the placebo-controlled and at Visit 1 (and as per the indications at Visit 2) of the open study;
- those who received two courses of therapy both in the placebo-controlled and at Visit 3 (and as per the indications at Visit 4) of the open study.

Inclusion criteria

The study will include patients who meet all these criteria:

- 1. Men and women over 50 years of age;
- 2. Signed informed consent form for the study participants;

3. Verified gonarthrosis according to ACR criteria (knee pain in combination with one of the following signs: age over 50 years, crepitation in the joint or morning stiffness in the joint lasting less than 30 minutes in combination with radiological signs of gonarthrosis);

4. II-III radiological stage of gonarthrosis according to the Kellgren-Lawrence classification with a predominant lesion of the medial tibiofemoral section of the knee joint;

5. Completion of participation in the IA/PAAG-SI/OA/2019 clinical trial in the group with NOLTREX[™] medical device through Visit 5 (25 weeks).

Non-inclusion criteria

Patients cannot be included in the study if they have at least one of the following criteria for noninclusion:

- 1. Pregnancy or breast-feeding;
- 2. History of injury or surgery on the target knee joint;
- 3. Instability of the target knee joint;
- 4. Microcrystalline arthropathies (according to anamnesis and taking into account clinical manifestations);
- 5. Systemic inflammatory diseases (rheumatoid arthritis, systemic lupus erythematosus, etc.);
- 6. Seronegative spondyloarthritis and reactive arthritis;
- 7. Increasing the level of rheumatoid factor;
- 8. Increased uric acid level > 360 mmol/l;
- 9. Intra-articular injection into the target knee joint:
 - hyaluronates within past 12 months before the patient is included in the study;
 - other synovial fluid endoprostheses (other than NOLTREX[™] in the IA/PAAG-SI/OA/2019 study) within past 24 months;
 - glucocorticosteroids within 1 month before inclusion in the study;
 - NSAIDs intra-articular administration at any time in the anamnesis.
- 10. Systemic painkillers (NSAIDs, opioid analgesics) within 1 week before the Visit 0;
- 11. Effusion in the target joint;
- 12. The presence of inflammation or infection in the target joint, synovitis;
- 13. The need for stable use of glucocorticosteroids in any dosage form;

- 14. Use of paracetamol within 48 hours before the Visit 0;
- 15. A positive blood test result for one or more of the following infections: HIV, viral hepatitis B and C, syphilis;
- 16. Severe liver pathology, defined as an increase in the level of one of the indicators: ALT, AST, ALP, total bilirubin, GGTP more than 3 times compared to the upper limit of the norm;
- 17. Kidney diseases with glomerular filtration rate when evaluated using the Cocraft-Gault formula less than 60 ml/min/1.73 m2 (chronic kidney disease stages III–V);
- 18. Clinically manifested coxarthrosis;
- Severe decompensated chronic or acute diseases and other conditions or other causes that, in the opinion of the research doctor, may hinder the patient's participation in the study or affect the results of the study;
- Participation in any other clinical trial other than the IA/PAAG-SI/OA/2019 trial within past
 90 days prior to inclusion in the study.

Exclusion criteria

In the following cases, patients will be excluded from the study:

- a. The Ethics Committee, regulatory authorities, or the Sponsor will terminate the study or participation in the study of this clinical center for any reason;
- b. The investigator decided that the patient should be excluded in the interests of the patient;
- c. Withdrawal of informed consent (unwillingness of the patient to continue participating in the study);
- d. Serious deviation from the research Protocol;
- e. Erroneous inclusion (for example, the patient was included in violation of the Protocol's inclusion/non-inclusion criteria);
- f. The patient receives/needs additional treatment that may affect the outcome of the study or the patient's safety (for more information, see the section "Prohibited concomitant therapy");
- g. Injury to the target knee joint;
- h. Other conditions or events that, in the opinion of the research doctor, require the patient to be excluded from the study.

If patients included in the study are found to have reasons for completing the study prematurely, they are excluded from the study at the stage of identifying these reasons. Each case of premature completion of the study by the patient or withdrawal of the patient from the study must be documented with the mandatory indication of the reason for premature completion/withdrawal from the study, as well as reporting to the Sponsor within 7 business days.

Prohibited concomitant therapy

- 1. Glucocorticosteroids in any dosage form;
- 2. Any intra-articular and periarticular injections;

3. Use of NSAIDs and painkillers that are not approved by the Protocol, including local ones (with the exception of paracetamol and NSAIDs allowed by the Protocol in case of ineffectiveness of paracetamol);

4. Use of paracetamol at a dose of more than 4000 mg per day;

5. Use of one of the Protocol-approved NSAIDs in doses exceeding the permitted doses (permitted drugs and doses: diclofenac potassium 50 mg 2 times a day, diclofenac sodium tablets 75 mg 2 times a day, naproxen tablets 500 mg 2 times a day, naproxen sodium tablets 550 mg 2 times a day, meloxicam tablets 7.5 mg once a day, celecoxib tablets 200 mg 2 times a day);

6. Use of a combination of paracetamol with NSAIDs or a combination of two or more NSAIDs;

7. Surgical interventions and arthroscopies on the target knee joint.

Justification of the sample size

This open-label MD NOLTREXTM safety assessment study includes eligible and non-eligible patients who received MD NOLTREXTM as part of the IA/PAAG-SI/OA/2019 study. Therefore, no formal calculation of the sample size was performed. The maximum expected number of study participants is the number of patients who were randomized to the MD NOLTREXTM group in the IA/PAAG-SI/OA/2019 study, i.e. 72 patients.

Blinding, randomization

This study is planned as an open-label study in a single group with subsequent division into subgroups depending on the actual need for treatment. In this regard, the Protocol does not provide for blinding and randomization.

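### The Group B rule for stopping after one injection is set at Visit 2, which Group B does not attend, and it disagrees with the Visit 4 procedure

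*Protocol*

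**What the plan says.** Under Study design, the Protocol states that the Group B course "is a maximum of 2 injections (the first - at Visit 3, the second - at Visit 4". Two sentences later it ends the course early for a good response, defined as "reducing the pain severity on a 100 mm VAS by Visit 2 by more than 40" per cent "compared to the basal level in the open study[1]), the course of injections will be discontinued". (The percent sign is garbled in the extracted text; I read it as percent.) The Group A paragraph of the same section contains the same sentence, and there the injections are at Visits 1 and 2.

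On attendance, Study design says that for these patients "a re-injection of MD NOLTREXTM will not be performed on Visits 1 and 2 of the open study (Group B". The Visit 2 entry under Patient visits says "Only patients who received an injection of MD NOLTREXTM into the target knee joint on Visit 1 are eligible for Visit 2".

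The visit procedures hold their own rules. At Visit 4, Group B receives the second injection only if VAS pain "did not decrease by 40% or more compared to the assessment at Visit 3". At Visit 2, Group A receives it only if VAS pain "did not decrease by 40% or more compared to the assessment on the Visit 0".

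**The concern.** The sentence decides whether a patient receives a second 4 mL. Its stated purpose is to keep the joint from being overfilled with a material that is cleared slowly, and the main purpose of the study is safety. For Group B it refers to a visit that these patients do not have, so it gives the site no usable instruction. A site that tries to repair it could change only the visit number and keep the open-study basal level as the reference. That would produce a rule different from the one in the Visit 4 procedure, and some patients would be given, or refused, a second injection contrary to that procedure.

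**Working it through.** **1. Can the Group B sentence be applied?** Group B is not injected at Visit 1, and only patients injected at Visit 1 attend Visit 2. Group B therefore has no Visit 2 VAS. Visit 2 is also Day 8 and Visit 3 is Day 84 (± 2), a gap of 84 − 8 = 76 days, or about 11 weeks. A Visit 2 value could not measure response to an injection first given at Visit 3.

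**2. The two Group B rules side by side.**

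| | Study design | Visit 4 procedure |
|---|---|---|
| Visit assessed | Visit 2 | Visit 4 |
| Reference | open-study basal level (footnote 1 not available) | Visit 3 |
| Stop if the fall is | more than 40% | 40% or more |

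The best guide to the reference is Group A. The identical sentence is carried out in the Visit 2 procedure against Visit 0, and the list of effectiveness parameters also places the open-study basal value at Visit 0. For Group A, the Study design sentence and the Visit 2 procedure then differ only at exactly 40%.

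**3. Direction of the difference if Visit 0 is used at Visit 4.** Write B for VAS at Visit 1 of the 2019 study, and V0, V3, V4 for VAS at Visits 0, 3 and 4 of the open study.

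- Entry to Group B through pain relief requires V0 ≤ 0.6B.
- Injection at Visit 3 requires V3 > 0.6B.
- Hence V3 > V0 for every such patient. Enumeration over whole-millimetre values gives 186,580 combinations of B, V0 and V3, none with V3 ≤ V0.

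The Visit 4 procedure stops the course at V4 ≤ 0.6 × V3. With Visit 0 as the reference, the cut-off is 0.6 × V0, which is lower. The fall from Visit 3 needed to stop becomes 1 − 0.6 × (V0/V3) instead of 40%:

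- V0/V3 = 0.9: 1 − 0.54 = 46%
- V0/V3 = 0.75: 1 − 0.45 = 55%
- V0/V3 = 0.5: 1 − 0.30 = 70%

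**4. Two worked cases (assumed VAS values in mm, not trial data).**

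*Pain-relief entry: B 60, V0 30, V3 45, V4 25.* V0 is 50% below B, so the patient enters Group B. V3 is 25% below B, so the patient is injected at Visit 3. From Visit 3 the fall is 1 − 25/45 = 44%, so the Visit 4 procedure stops the course. From Visit 0 it is 1 − 25/30 = 17%, so the course continues. The cut-offs are 0.6 × 45 = 27 and 0.6 × 30 = 18.

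*Entry because injection was not possible: B 70, V0 65, V3 45, V4 35.* V3 is 36% below B, so the patient qualifies for injection once the bar has cleared. From Visit 3 the fall is 1 − 35/45 = 22%, so the Visit 4 procedure injects. From Visit 0 it is 1 − 35/65 = 46%, so the course stops. The cut-offs are 27 and 0.6 × 65 = 39. In this route the disagreement can run either way.

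**5. The boundary.** On a whole-millimetre scale, an exact 40% fall exists only when the reference is a multiple of 5 mm, for example 50 to 30 mm. Only then does the wording at the boundary matter.

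**The case against.** The strongest reply is that the protocol already contains the right rule. The Visit 4 procedure states the visit, the reference and the threshold, and a site conducting Visit 4 would probably work from that list. The Study design sentence cannot be applied at all, so it hardly competes. This stands, and it is why the matter is minor. It does not remove the contradiction, because nothing says which text prevails.

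Second, the Visit 0 percentages need a reading that no text states for Group B: the visit corrected to 4, the reference left at Visit 0, and the Visit 4 procedure set aside. Footnote 1 may define the basal level as Visit 3 for Group B. This also stands. The percentages and both cases are conditional illustrations. If the footnote sets Visit 3, only the wrong visit and the boundary remain.

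Third, entry because injection was not possible is a narrow route. Diabetes, past thrombosis or documented intolerance would normally still bar injection at Visit 3, and joint effusion or inflammation already prevents inclusion. Mainly transient laboratory findings, skin inflammation, recent infection or stopped anticoagulants remain. That is fair, and it limits how often the second case could arise.

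Fourth, the course is capped at two injections, the doctor has discretion over the number, and the analysis subgroup pools patients given one or two injections from Visit 3. All true. The point therefore concerns dosing instructions, not an estimate or a subgroup definition.

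**Conclusion.** The point holds. The Group B stopping sentence in Study design is wrong as written: it names a visit Group B does not have, and it differs from the Visit 4 procedure in visit and in the boundary at 40%. Those findings do not depend on the missing footnote. The difference in reference value is likely but rests on reading the open-study basal level as Visit 0.

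The size is small. The effect is nil if sites follow the Visit 4 procedure, and the documents give no basis for counting affected patients. If Visit 0 were used at Visit 4, every patient in Group B through pain relief would face a stricter condition for stopping, so second injections could only become more frequent among them. For the other route the direction is open.

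**What to change.** In Study design, replace the Group B sentence with: the course is stopped if VAS pain at Visit 4 has fallen by 40% or more from Visit 3. In the Group A paragraph, write the criterion as a fall of 40% or more from Visit 0 by Visit 2, so that it matches the Visit 2 procedure. The Visit 2 and Visit 4 procedures stay as they are. One rule then remains for Group B: give the second injection if V4 > 0.6 × V3.

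The cost is one sentence and one phrase. The item "Assessment of the severity of pain in the target knee joint using 100-mm VAS" is already on the procedure lists for Visits 3 and 4, so no visit, procedure or analysis is added.
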